### **13.7 Publications and Clinical Study Report**

#### **13.7.1 Publication of Study Results**

Vertex is committed to reporting the design and results of all clinical studies in a complete, accurate, balanced, transparent, and timely manner, consistent with Good Publication Practices (GPP3).

**Publication Planning:** Vertex staff along with the lead PIs, the steering committee, and/or the publication committee will work together to develop a publication plan.

**Authorship:** Authorship of publications will be determined based on the Recommendations for Conduct, Reporting, Editing, and Publication of Scholarly Work in Medical Journals, which states that authorship should be based on the following 4 criteria:

1. Substantial contributions to conception and design, acquisition of data, or analysis and interpretation of data;
2. Drafting of the article or revising it critically for important intellectual content;
3. Final approval of the version to be published; and
4. Agreement to be accountable for all aspects of the work in ensuring that questions related to the accuracy or integrity of any part of the work are appropriately investigated and resolved.

All authors must meet conditions 1, 2, 3, and 4. All persons designated as authors should qualify for authorship, and all those who qualify should be listed. Contributions such as medical writing, enrollment of subjects, acquisition of funding, collection of data, or general supervision of the research group, alone, do not justify authorship.

**Contributors:** Contributors who meet fewer than all 4 of International Committee of Medical Journal Editors (ICMJE) criteria for authorship will not be listed as authors, but their contribution will be acknowledged and specified either as a group (e.g., “study investigators”) or individually (e.g., “served as scientific advisor”).

**Publication Review:** As required by a separate clinical study agreement, Vertex must have the opportunity to review all publications, including any manuscripts, abstracts, oral/slide presentations, and book chapters regarding this study before submission to congresses or journals for consideration.

### **13.7.2 Clinical Study Report**

A CSR, written in accordance with the current ICH E3 Guideline, will be submitted in accordance with local regulations.

## APPENDIX A: EXAMPLES OF ELIGIBLE MF MUTATIONS

“MF” mutations are a subset of minimal function mutations that are non-responsive to TEZ, IVA, or TEZ/IVA. A mutation is considered an MF mutation if it meets at least 1 of the following 2 criteria:

- (1) biological plausibility of no translated protein (genetic sequence predicts the complete absence of CFTR protein), or
- (2) in vitro testing that supports lack of responsiveness to TEZ, IVA, or TEZ/IVA

### Inclusion of MF Mutations Based on In Vitro Testing

Mutations that were considered to be MF mutations based on in vitro testing met the following criteria in in vitro experiments:

- baseline chloride transport that was <10% of wildtype CFTR
- an increase in chloride transport of <10% over baseline following the addition of TEZ, IVA, or TEZ/IVA in the assay

### Eligible MF Mutations

The list below represents acceptable mutations, which are detectable by an FDA-cleared genotyping assay or other method (e.g., sequencing); however, this list does not include every eligible mutation, and investigators should contact the medical monitor regarding other mutations that may also meet study eligibility criteria.

#### Examples of Eligible MF Mutations for VX20-121-102

MF Mutation Category	Mutation					
Nonsense mutations	Q2X	L218X	Q525X	R792X	E1104X	
	S4X	Q220X	G542X	E822X	W1145X	
	W19X	Y275X	G550X	W882X	R1158X	
	G27X	C276X	Q552X	W846X	R1162X	
	Q39X	Q290X	R553X	Y849X	S1196X	
	W57X	G330X	E585X	R851X	W1204X	
	E60X	W401X	G673X	Q890X	L1254X	
	R75X	Q414X	Q685X	S912X	S1255X	
	L88X	S434X	R709X	Y913X	W1282X	
	E92X	S466X	K710X	Q1042X	Q1313X	
	Q98X	S489X	Q715X	W1089X	Q1330X	
	Y122X	Q493X	L732X	Y1092X	E1371X	
	E193X	W496X	R764X	W1098X	Q1382X	
	W216X	C524X	R785X	R1102X	Q1411X	
	Canonical splice mutations	185+1G→T	711+5G→A	1717-8G→A	2622+1G→A	3121-1G→A
		296+1G→A	712-1G→T	1717-1G→A	2790-1G→C	3500-2A→G
296+1G→T		1248+1G→A	1811+1G→C	3040G→C	3600+2insT	
405+1G→A		1249-1G→A	1811+1.6kbA→G	(G970R)	3850-1G→A	
405+3A→C		1341+1G→A	1811+1643G→T	3120G→A	4005+1G→A	
406-1G→A		1525-2A→G	1812-1G→A	3120+1G→A	4374+1G→T	
621+1G→T		1525-1G→A	1898+1G→A	3121-2A→G		
711+1G→T			1898+1G→C			

### Examples of Eligible MF Mutations for VX20-121-102

MF Mutation Category	Mutation				
Small ( $\leq 3$ nucleotide) insertion/deletion (ins/del) frameshift mutations	182delT	1078delT	1677delTA	2711delT	3737delA
	306insA	1119delA	1782delA	2732insA	3791delC
	306delTAGA	1138insG	1824delA	2869insG	3821delT
	365-366insT	1154insTC	1833delT	2896insAG	3876delA
	394delTT	1161delC	2043delG	2942insT	3878delG
	442delA	1213delT	2143delT	2957delT	3905insT
	444delA	1259insA	2183AA→G a	3007delG	4016insT
	457TAT→G	1288insTA	2184delA	3028delA	4021dupT
	541delC	1343delG	2184insA	3171delC	4022insT
	574delA	1471delA	2307insA	3171insC	4040delA
	663delT	1497delGG	2347delG	3271delGG	4279insA
	849delG	1548delG	2585delT	3349insT	4326delTC
	935delA	1609del CA	2594delGT	3659delC	
	Non-small ( $> 3$ nucleotide) insertion/deletion (ins/del) frameshift mutations	CFTRdele1	CFTRdele16-17b		1461ins4
CFTRdele2		CFTRdele17a,17b		1924del7	
CFTRdele2,3		CFTRdele17a-18		2055del9→A	
CFTRdele2-4		CFTRdele19		2105-2117del13insAGAAA	
CFTRdele3-10,14b-16		CFTRdele19-21		2372del8	
CFTRdele4-7		CFTRdele21		2721del11	
CFTRdele4-11		CFTRdele22-24		2991del32	
CFTR50kdel		CFTRdele22,23		3121-977_3499+248del2515	
CFTRdup6b-10		124del23bp		3667ins4	
CFTRdele11		602del14		4010del4	
CFTRdele13,14a		852del22		4209TGTT→AA	
CFTRdele14b-17b	991del5				
Missense mutations that • Are non-responsive in vitro to TEZ, IVA, or TEZ/IVA	A46D	V520F	Y569D	N1303K	
	G85E	A559T	L1065P		
	R347P	R560T	R1066C		
	L467P	R560S	L1077P		
	I507del	A561E	M1101K		

IVA: ivacaftor; MF: minimal function; SwCl: sweat chloride; TEZ: tezacaftor

Source: CFTR2.org [Internet]. Baltimore (MD): Clinical and functional translation of CFTR. The Clinical and Functional Translation of CFTR (CFTR2), US Cystic Fibrosis Foundation, Johns Hopkins University, the Hospital for Sick Children. Available at: <http://www.cftr2.org/>. Accessed 15 February 2016.

a Also known as 2183delAA→G.

2 MODIFICATIONS

2.1 Modifications to the Approved Clinical Study Protocol

Not Applicable.

2.2 Modifications to the Approved Statistical Analysis Plan

This is the first version of the Statistical Analysis Plan.

2.3 Modifications to the Approved DMC Charter

Not Applicable.

3 INTRODUCTION

This statistical analysis plan (SAP) is the planned statistical analysis for Study VX20-121-102 (Study 102) and is based on the most recent approved clinical study protocol (CSP), the most recent approved electronic case report form (eCRF), and the most recent eCRF completion guidelines.

Study 102 is a Phase 3, randomized, double-blind, elexacaftor/tezacaftor/ivacaftor (ELX/TEZ/IVA)-controlled, parallel group, multicenter study evaluating the efficacy and safety of vanzacaftor (VX-121)/tezacaftor/deutivacaftor (VNZ/TEZ/D-IVA) in cystic fibrosis (CF) subjects who are heterozygous for *F508del* and a minimal function mutation (F/MF). This SAP (Methods) documents the planned final analyses and data presentation for Study 102. For some of these analyses, the Study 102 data are pooled with data from Study VX20-121-103 (Study 103) which is running in parallel with a similar study design and aims to evaluate similar outcomes using a different patient population.

The Vertex Pharmaceuticals Incorporated (Vertex) Biometrics Department will perform the statistical analysis of the efficacy and safety data. SAS® Version 9.4 Software (SAS Institute, Cary, North Carolina, USA) or higher will be used to generate all statistical outputs (tables, figures, listings, and datasets).

The SAP (Methods) will be finalized and approved prior to clinical database lock and treatment unblinding. Any revisions to the approved SAP will be documented and approved in an amendment to the SAP prior to the clinical database lock.

The analysis addressing the pharmacokinetic (PK) objective of the study will be described in the Clinical Pharmacology Analysis Plan which will be developed separately by the Clinical Pharmacology department at Vertex.

4 STUDY OBJECTIVES

4.1 Primary Objective

To evaluate the efficacy of VNZ/TEZ/D-IVA in CF subjects who are heterozygous for *F508del* and a minimal function mutation (F/MF subjects)

4.2 Secondary Objectives

- To evaluate the safety of VNZ/TEZ/D-IVA
- To evaluate the PK of VNZ/TEZ/D-IVA

5 STUDY ENDPOINTS

5.1 Primary Endpoint

Absolute change from baseline in percent predicted forced expiratory volume in 1 second (ppFEV₁) through Week 24

5.2 Key Secondary Endpoints

- Absolute change from baseline in sweat chloride (SwCl) through Week 24

- Proportion of subjects with SwCl <60 mmol/L through Week 24 (pooled with data from Study 103)
- Proportion of subjects with SwCl <30 mmol/L through Week 24 (pooled with data from Study 103)

5.3 Other Secondary Endpoints

- Number of pulmonary exacerbations (PEX) through Week 52
- Absolute change from baseline in Cystic Fibrosis Questionnaire – Revised (CFQ-R) Respiratory Domain (RD) score through Week 24
- Absolute change from baseline in ppFEV₁ through Week 52
- Absolute change from baseline in SwCl through Week 52
- Proportion of subjects with SwCl <60 mmol/L through Week 24
- Proportion of subjects with SwCl <30 mmol/L through Week 24
- Safety and tolerability assessments based on adverse events (AEs), clinical laboratory values, electrocardiograms (ECGs), vital signs, and pulse oximetry

5.4 Other Endpoints

[figure not shown]
- Proportion of subjects with SwCl <60 mmol/L through Week 52
- Proportion of subjects with SwCl <30 mmol/L through Week 52
- Absolute change from baseline in body mass index (BMI) at Week 52
- Absolute change from baseline in BMI z-score at Week 52
- Absolute change from baseline in weight at Week 52
- Absolute change from baseline in CFQ-R RD score through Week 52
- PK parameters of VNZ, TEZ, and D-IVA

6 STUDY DESIGN

6.1 Overall Design

Study 102 is a Phase 3, randomized, double-blind, ELX/TEZ/IVA-controlled, parallel-group, multicenter study. A schematic of the study design is provided in [Figure 6-1](#).

Figure 6-1 Schematic View of the Study Design

D-IVA: deutivacaftor; ELX: elexacaftor; IVA: ivacaftor; TEZ: tezacaftor; VNZ: vanzacaftor
 Note: The figure is not drawn to scale.

Approximately 400 subjects will be enrolled and randomized.

All subjects entering the Run-in Period will receive ELX 200 mg once daily (qd)/TEZ 100 mg qd/IVA 150 mg every 12 hours (q12h). Following completion of the Run-in Period, subjects will be randomized (1:1) to the VNZ/TEZ/D-IVA group or the ELX/TEZ/IVA group for the Treatment Period. The dosages to be evaluated are shown in Table 6-1. Randomization will be stratified; details are provided in 6.3.

Table 6-1 Treatment Groups and Dosages

Treatment Group	VNZ	ELX	TEZ	D-IVA	IVA
VNZ/TEZ/D-IVA	20 mg qd	0 mg	100 mg qd	250 mg qd	0 mg
ELX/TEZ/IVA	0 mg	200 mg qd	100 mg qd	0 mg	150 mg q12h

D-IVA: deutivacaftor, ELX: elexacaftor, IVA: ivacaftor; q12h: every 12 hours; qd: once daily; TEZ: tezacaftor; VNZ: vanzacaftor

6.2 Sample Size and Power

6.2.1 Power for Primary Analysis of Primary Efficacy Endpoint

The primary efficacy endpoint is the absolute change from baseline in ppFEV₁ through Week 24. The primary null hypothesis to be tested is that the mean absolute change in ppFEV₁ from baseline through Week 24 for VNZ/TEZ/D-IVA is inferior by >3 percentage points compared to ELX/TEZ/IVA.

The non-inferiority margin represents a clinically acceptable loss of effectiveness as outlined in regulatory guidances. Furthermore, a statistical approach using the Rothmann method recommends that the non-inferiority margin preserve at least 50% of the treatment effect of the active control (ELX/TEZ/IVA) compared to placebo, where the treatment effect is estimated by the lower bound of the 95% confidence interval (CI)^{1,2}. In the overall population eligible for this

study, the lower bound of the 95% CI of the treatment effect for ELX/TEZ/IVA is approximately 12 percentage points for ppFEV₁. The selected non-inferiority margin of 3 percentage points is consistent with this statistical method and the non-inferiority margin for ppFEV₁ used in clinical studies evaluating symptomatic CF treatments^{3,4}.

The null hypothesis will be tested at a 1-sided significance level of 0.025.

Assuming a within-group standard deviation (SD) of 8 and a 10% drop-out rate at Week 24 and a treatment difference of 0 between VNZ/TEZ/D-IVA and ELX/TEZ/IVA, a sample size of 200 subjects in each group for a total of 400 subjects will have more than 90% power to test the primary hypothesis for the primary endpoint, based on a 1-sided, 2-sample *t*-test at a significance level of 0.025.

6.2.2 Power for Analysis of Selected Key Secondary Efficacy Endpoint

A key secondary efficacy endpoint is the absolute change from baseline in SwCl through Week 24. Assuming a within-group SD of 14 mmol/L and a 10% drop-out rate at Week 24, a sample size of 200 subjects in each treatment group will have more than 90% power to detect a difference between the treatment groups of -5 mmol/L for the absolute change from baseline in SwCl through Week 24, based on a 2-sided, 2-sample *t*-test at a significance level of 0.05.

6.3 Randomization

Approximately 400 subjects will be randomized (1:1) to the VNZ/TEZ/D-IVA group or the ELX/TEZ/IVA group. Randomization will be stratified by age at the Screening Visit (<18 versus ≥18 years of age), ppFEV₁ determined during the Run-in Period (Day -14 clinic assessment; <70 versus ≥70 percentage points), SwCl determined during the Run-in Period (Day -14 assessment; <30 versus ≥30 mmol/L), and prior CFTR modulator use (yes versus no).

6.4 Blinding and Unblinding

This is a double-blind study. Please refer to Section 10.7 of the Study 102 CSP for details.

7 ANALYSIS SETS

7.1 All Subjects Set

The **All Subjects Set** will include all subjects who were randomized or received at least 1 dose of study drug. This analysis set will be used for all individual subject data listings and disposition summary tables, unless otherwise specified.

7.2 Full Analysis Set

The **Full Analysis Set** (FAS) will include all randomized subjects who carry the intended *CFTR* genotype and received at least 1 dose of study drug during the Treatment Period. The FAS will be used to summarize subject demographics and baseline characteristics and for analyses of all efficacy endpoints in which subjects will be analyzed according to their randomized treatment group, unless otherwise specified.

7.3 Pooled Full Analysis Set

The **Pooled Full Analysis Set** (PFAS) will include all randomized subjects from this study (Study 102) and from Study 103 who carry the intended *CFTR* genotype and received at least 1

dose of study drug during the Treatment Period. The PFAS will be used only for pooled analysis of selected endpoints.

7.4 Safety Set

The **Safety Set for the Run-in Period** will include all subjects who received at least 1 dose of ELX/TEZ/IVA during the Run-in Period. This safety set will be used for safety-related outputs during the Run-in Period, unless otherwise specified.

The **Safety Set for the Treatment Period** will include all subjects who received at least 1 dose of study drug during the Treatment Period. This safety set will be used for all safety analyses during the Treatment Period in which subjects will be analyzed according to the treatment they actually received, unless otherwise specified.

8 STATISTICAL ANALYSIS

8.1 General Considerations

The Schedule of Assessments is provided in the CSP for Study 102. The precision standards for reporting safety and efficacy variables are provided in an internal Biometrics document that specifies the programming rules including the precision for derived variables.

Continuous variables will be summarized using the following descriptive summary statistics: the number of subjects (n), mean, SD, median, minimum value (min), and maximum value (max).

Categorical variables will be summarized using counts and percentages. Percentages will be presented to 1 decimal place.

Baseline value:

For all safety endpoints:

- Unless otherwise specified, baseline will be defined as the most recent non-missing measurement (scheduled or unscheduled) collected before the first dose of study drug in the Treatment Period (i.e., the Day 1 Visit).

For all efficacy endpoints:

- Except for SwCl, baseline will be defined as the pre-dose Day 1 value. If the pre-dose Day 1 value is missing, the most recent pre-dose, non-missing value on or after the Day -14 visit, including unscheduled visits, will be used as baseline.
- For SwCl, baseline will be defined as the average of the two most recent pre-dose, non-missing values on or after the Day -14 visit, including unscheduled visits. If only 1 non-missing value is available during this interval, the available value will be considered as baseline.

Absolute change from baseline will be calculated as post-baseline value - baseline value.

Relative change from baseline will be calculated as (post-baseline value - baseline value)/baseline value.

The **Treatment-emergent (TE) Period for the Run-in Period** will be from the first dose date of study drug in the Run-in Period to (1) the first dose date of study drug in the Treatment Period for subjects who complete the Run-in Period and continue to the Treatment Period, or (2) 28 days after the last dose date of study drug in the Run-in Period or to the completion of study participation date, whichever occurs first, for subjects who do not continue to the Treatment Period (e.g., subjects who do not meet the conditions to enter the Treatment Period).

The **TE Period for the Treatment Period** will be from the first dose date of study drug in the Treatment Period (VNZ/TEZ/D-IVA or ELX/TEZ/IVA) to 28 days after the last dose date of study drug in the Treatment Period or to the completion of study participation date, whichever occurs first.

The **PEx analysis period through Week 52** will be from the first dose date of study drug in the Treatment Period to the last efficacy assessment, which may be collected up to the Week 52 Visit or the earlier of Day 365 and the completion of study participation date if a subject does not have the Week 52 Visit.

Unscheduled visits: Unscheduled visit measurements will be included in analysis as follows:

- 1) In scheduled visit windows per specified visit windowing rules
- 2) In the derivation of baseline and last on-treatment measurements
- 3) In the derivation of maximum and minimum values and maximum and minimum change from baseline values during the TE Period for the Treatment Period for safety analyses
- 4) In individual subject data listings as appropriate

Visit windowing rules: The analysis visit windows for protocol-defined visits are provided in [Appendix](#) .

Incomplete/missing data: Details on how to handle missing data are described in subsequent sections when applicable.

Outliers: No formal statistical analyses will be performed to detect or remedy the presence of statistical outliers, unless otherwise specified.

Multiplicity: The multiplicity adjustment procedure for the primary and key secondary endpoints is described in [8.3.2.3](#). All other *P* values are nominal.

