### 9.1.2 ELX/TEZ/IVA Run-in Period

The Run-in Period has a 4-week duration and is designed to establish a reliable on-treatment (ELX/TEZ/IVA) baseline for the Treatment Period. The first dose of open-label ELX/TEZ/IVA will be administered at the Day -28 Visit. Female subjects must have a negative pregnancy test at Day -28 before receiving study drug. The last dose of open-label ELX/TEZ/IVA will be administered on Day -1 (1 day before the Day 1 Visit).

On Day -14, spirometry (clinic and mobile) and SwCl will be assessed. The Day -14 clinic spirometry and SwCl assessments will be used for stratification of randomization (Section 9.2).

Subjects who prematurely discontinue study drug treatment during the Run-in Period will not be randomized or participate in the Treatment Period (Section 9.1.5.1).

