### 9.1.8 Use of Remote Measures in Extenuating Circumstances

Study visits should be performed in the clinic as specified in Section 3, Table 3-1, and Table 3-2, if at all possible. However, under extenuating circumstances, specific alternative measures may be implemented (e.g., if a subject is unable to travel to the study site due to safety concerns and/or local restrictions related to COVID-19 or other emerging events) in order to ensure the safety of subjects, site investigators, and site personnel while maintaining compliance with GCP and minimizing impact to the integrity of the study. The decision whether to conduct study visits remotely or in clinic will be at the discretion of the investigator; if the investigator determines that study visits will be conducted remotely, the medical monitor should be notified. The Screening Visit, Day -28 Visit, Day -14 Visit, Day 1 Visit, Week 24 Visit, and Week 52 Visit must be performed in clinic.

The following remote measures may be implemented. Additional details can be found in the Study Reference Manual.

- Consent or re-consent may be obtained remotely in writing (or verbally, with follow-up written confirmation), as allowed by local regulations.
- Study drug may be shipped directly from the site to the subject, as applicable and as allowed by local regulations.
- Study visits (except for those noted above) may be conducted as in-home visits by qualified personnel.
- Study assessments to evaluate safety and efficacy may be performed or overseen by qualified personnel conducting the in-home visits.

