## 9.2 Method of Assigning Subjects to Treatment Groups

Subjects will be randomized (1:1) to the VX-121/TEZ/D-IVA group or the ELX/TEZ/IVA group. Randomization will be stratified by age at the Screening Visit (<18 versus  $\geq$ 18 years of age), ppFEV1 determined during the Run-in Period (Day -14 clinic assessment; <70 versus  $\geq$ 70), SwCl determined during the Run-in Period (Day -14 assessment; <30 versus  $\geq$ 30 mmol/L), and prior CFTR modulator use (yes versus no). If the Day -14 ppFEV1 and/or SwCl values are not valid or not available, the most recent available clinic-assessed ppFEV1 and/or SwCl value will be used for stratification.

An interactive web response system (IWRS) will be used to assign subjects to treatment. The randomization code list will be produced by Vertex Biometrics or a qualified randomization vendor.

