8.3.1.3 Primary Analysis

The primary null hypothesis to be tested is that the mean for the primary efficacy variable for VNZ/TEZ/D-IVA is inferior by >3 percentage points compared to ELX/TEZ/IVA. The primary analysis of the primary estimand will be performed using a mixed-effects model for repeated measures (MMRM) with change from baseline at Day 15, Week 4, Week 8, Week 16, and Week 24 as the dependent variable. The model will include fixed categorical effects for treatment, visit, age at screening (<18 versus ≥18 years of age), and treatment-by-visit interaction, with baseline ppFEV₁ and baseline SwCl as continuous covariates. The model will be estimated using restricted maximum likelihood. Denominator degrees of freedom for the *F*-test for fixed effects will be estimated using the Kenward-Roger approximation⁵. An unstructured covariance structure will be used to model the within-subject errors. If the model estimation does not converge, an alternative covariance structure like compound symmetry will be used. Conditional on the observed data and covariates, missing data will be assumed to be missing at random (MAR).

The primary result obtained from the model will be the estimated treatment difference through Week 24 (estimated by averaging Weeks 16 and 24). The adjusted mean with a 2-sided 95% CI and the 1-sided *P* value for non-inferiority will be provided. The primary null hypothesis will be rejected, and non-inferiority demonstrated, if the lower bound of the CI is ≥-3.0.

The primary null hypothesis of non-inferiority described above will be tested based on the FAS.

If non-inferiority for the primary endpoint is demonstrated, and if the lower bound of the same 95% CI is greater than 0, then superiority for the primary endpoint is also demonstrated, and the 2-sided *P* value for superiority will be presented.

The estimated within-group change from baseline and treatment difference at each post-baseline visit, obtained from the model, will be provided. The estimated within-group change and its standard error (SE) at each post-baseline visit will also be plotted by treatment group.

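### The primary ppFEV1 model leaves out the Day -14 clinic ppFEV1, a pre-randomization covariate already scheduled for all subjects; adding it would tighten the CI at almost no cost

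*SAP*

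**What the plan says.** **Baseline.** SAP 8.1 sets the ppFEV1 baseline at one visit: "Except for SwCl, baseline will be defined as the pre-dose Day 1 value". An earlier run-in measurement enters only when Day 1 is missing, in which case "the most recent pre-dose, non-missing value on or after the Day -14 visit, including unscheduled visits, will be used as baseline". The same section treats sweat chloride differently: "For SwCl, baseline will be defined as the average of the two most recent pre-dose, non-missing values on or after the Day -14 visit".

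**Model.** SAP 8.3.1.3 lists the terms: "The model will include fixed categorical effects for treatment, visit, age at screening" and treatment-by-visit, "with baseline ppFEV₁ and baseline SwCl as continuous covariates". Protocol 12.3.3.1 and the synopsis give the same covariates. Day -14 ppFEV1 does not appear, either as a continuous term or as the <70/≥70 stratum.

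**Availability.** Protocol 9.1.2 schedules the measurement for subjects on open-label ELX/TEZ/IVA: "On Day -14, spirometry (clinic and mobile) and SwCl will be assessed". Protocol 9.1.8 does not allow that visit to be remote: "The Screening Visit, Day -28 Visit, Day -14 Visit, Day 1 Visit, Week 24 Visit, and Week 52 Visit must be performed in clinic". Protocol 9.2 uses the Day -14 result to stratify randomization and provides for Day -14 results that "values are not valid or not available".

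**The concern.** Protocol 9.1.2 and 9.3.1 justify the run-in by the need for a dependable baseline on the control regimen. Two clinic spirometry sessions are scheduled in that period, and the primary model uses one of them. A single session carries visit-to-visit noise, so Day 1 ppFEV1 is an imperfect measure of the subject's underlying level, and the part it misses stays in the residual variance. A second pre-randomization value recovers some of that information.

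At stake is the width of the one 95% CI that decides non-inferiority at -3 and then superiority at 0. The ppFEV1 analysis through Week 52, the hypothetical-strategy supplementary analysis and the subgroup analyses all take their model from the primary one.

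**Working it through.** **1. The plan's own figure.** Inputs from SAP 6.2.1: margin 3, SD 8, true difference 0, 200 per arm, 10% drop-out, one-sided 0.025. Evaluable per arm: 200 × 0.9 = 180. SE = 8 × √(2/180) = 0.843. Power ≈ Φ(3/0.843 − 1.96) = Φ(1.60) = 94.5% (94.4% by noncentral t). The stated figure of more than 90% is met. The 95% CI half-width is 1.967 × 0.843 = 1.66.

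**2. Model for the gain (assumed).** The documents supply only the SD of 8, taken here as the SD of the change from Day 1 to the Week 16/24 mean. Each ppFEV1 value is a stable subject level (between-subject SD 12 or 15), plus slow drift with correlation exp(−days/τ) (τ = 60 or 180 days), plus independent visit noise. The total within-subject variance W is scaled so that the change has SD 8. The calculation is an ANCOVA on the Week 16/24 mean, as an approximation to the MMRM.

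**3. Formula.** Let M be the Week 16/24 mean, v the variance of one visit, c₁ and c₋₁₄ the covariances of M with Day 1 and Day -14, and r the correlation of the two run-in values.
- Given Day 1 only: Var(M) − c₁²/v
- Further reduction from Day -14: (c₋₁₄ − r·c₁)² / [v(1 − r²)]

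**4. Worked case: between-subject SD 15, τ = 60, half of W visit noise.**
- W = 64/1.4906 = 42.94, so v = 225 + 42.94 = 267.94.
- Covariance of the run-in values, 14 days apart: 225 + 21.47 × exp(−14/60) = 242.00, so r = 0.9032.
- Var(M) = 250.69, c₁ = 227.31, c₋₁₄ = 226.83.
- Day 1 only: 250.69 − 227.31²/267.94 = 57.84, SD 7.61.
- Reduction: (226.83 − 205.31)²/49.36 ≈ 9.38. With both values: 48.46, SD 6.96.
- Variance ratio: 48.46/57.84 = 0.838, a cut of about 16%.
- CI half-width (1.967 × SD × √(2/180)): 1.58 to 1.44.
- Non-inferiority power: 96.2% to 98.3%. Power for superiority at an assumed true +2: 70% to 78%.

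**5. Range over between-subject SD 12-15 and τ 60-180.**

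| Visit noise, share of W | Cut in residual variance |
|---|---|
| none | about 1-5% (below 1% at τ = 180) |
| 10% | 4-7% |
| half | 15-17% |
| all | 26-29% |

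In the 10% row the effect is small. With SD 15 and τ = 180, for example, the half-width goes from 1.59 to 1.56 and non-inferiority power from 95.8% to 96.5%.

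**6. Cross-check of the last row.** With no drift, all visits share one correlation ρ and the ratio is (1+3ρ)/[(1+ρ)(1+2ρ)]. For SD 15, W = 64/1.5 = 42.67 and ρ = 225/267.67 = 0.841. The ratio is 3.522/(1.841 × 2.681) = 0.714, a cut of 28.6%. For SD 12, ρ = 0.771 and the cut is 26.4%. A pure first-order Markov process with no visit noise gives a ratio of 1.00, hence no gain.

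**The case against.** **Nothing is broken.** Adjusting for Day 1 alone is a valid, pre-specified choice, given consistently in the protocol and SAP. A reader might infer from the omission that the trial is underpowered or the analysis wrong. The documents do not support that: the non-inferiority power claim is met, and no power is claimed for ppFEV1 superiority. The +2 used above is an assumption. This part of the objection stands.

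**The size is not anchored.** A reader might take the worked case as a gain equal to about 477 subjects instead of 400 (400 × 57.84/48.46). That rests on an assumed noise share and an assumed between-subject SD. The documents support only the range, whose lower end is close to nothing. This also stands.

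**Modulator-naive subjects may still be improving at Day -14.** Inclusion criterion 6 admits subjects not on ELX/TEZ/IVA. For them Day -14 falls about two weeks into the run-in, and the visit window runs from Day -15 to Day -3. This is a sound argument against averaging Day -14 into the baseline, and so against inferring from the sweat chloride rule that ppFEV1 must be averaged too. It does not count against a covariate: the outcome stays change from Day 1, and adjusting for a pre-randomization value does not bias the contrast. It does reduce the gain. As an illustration, suppose 30-50% of subjects are naive, with an extra Day -14 deviation of mean 4 and SD 6 (all assumed). The cut then falls to about 10-14% at half noise and 2-4% at 10% noise.

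**Not every subject will have a usable value.** Protocol 9.2 foresees this. Its fallback, the latest clinic value, suits stratification but not this covariate. No clinic spirometry is scheduled at Day -28, so the fallback could be a Screening value, which may be off ELX/TEZ/IVA and post-bronchodilator (protocol 11.5.1). This stands and shapes the fix.

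**Conclusion.** The point holds as an efficiency recommendation. Day -14 clinic ppFEV1 is measured before randomization on the control regimen and is left out of the primary model, and neither document gives a reason. Adding it would leave the outcome and the SAP 8.3.1.2 estimand unchanged and would normally narrow the CI. Under the assumed variance model the cut in residual variance lies between about 1% and 29%, depending on how much single-visit noise ppFEV1 carries, and is lower if many naive subjects are unstable at Day -14. The benefit to non-inferiority is small because power is already about 94%. It is more useful for CI width and for superiority.

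**What to change.** - In SAP 8.3.1.3, keep change from Day 1 as the outcome and Day 1 ppFEV1 as a covariate, and add Day -14 clinic ppFEV1 as a further continuous covariate. Carry it into the ppFEV1 model through Week 52 (8.3.3.2) and the supplementary model (8.3.1.4).
- State a rule for a missing or invalid Day -14 value that is blind to treatment and uses run-in data only, for example imputing the covariate from Day 1 ppFEV1. Do not substitute a Screening value. Note that when Day 1 is missing, SAP 8.1 may already make the Day -14 value the baseline, so the two covariates would coincide for that subject.
- Record the change in SAP 2.1, which now declares no modification, as a departure from the covariate list in protocol 12.3.3.1. Do this before database lock and unblinding, because afterwards it would look post hoc.

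Cost: one degree of freedom, one missing-covariate rule and one documented change to the protocol's model. No new data or visits are needed.
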